9.1.6 Medical History and Concomitant Diseases

The medical history and concomitant diseases tables will summarize the number and percentage of subjects reporting each medical history events by system organ class.

Analysis Population(s):	All Treated Confirmed Influenza
Derived Variables:	
 • Medical history classification = events with stop dates prior to screening date • Concomitant disease classification = events with stop dates on or after the date of the first administration of study drug until the end of the study

9.1.7 Treatment Exposure

The treatment exposure tables will summarize the total number of days on therapy and number of tablets taken using descriptive statistics.

Analysis Population(s):	All Treated Confirmed Influenza
Derived Variables:	Number of tablets taken = number of doses reported to have been taken on the diary * 2

9.2 General Characteristics Listings

General characteristics listings will include data specified in Table 4 for all subjects presented by subject number and treatment group.

Table 4. Data Presented in General Listings

Listing	Data Presented
Discontinued Subjects	Date of discontinuation Reason for discontinuation
Subjects with Protocol Deviations	Date of deviation Common deviation term Treatment stopped (Y/N) Subject discontinued (Y/N)

Listing	Data Presented
	Classification (Major/Minor/GCP)
Subjects Excluded from Efficacy Analysis ¹	Reason for exclusion
Demographic Data	Date/time of informed consent Date of birth Age Sex Race Height (cm) Weight (kg) BMI (kg/m ²) Smoking status Number of years smoked Number of cigarettes smoked per day Vaccination status (Y/N)
Baseline Disease Characteristics	Oral temperature in office (°F) Highest oral temperature (°F) Time from onset of symptoms to first study drug intake (hours) Virus infection(s) Respiratory symptoms Constitutional symptoms
Prior Medication Concomitant Medication	Reported medication term Standard medical name Level 4 ATC term Indication Start date Stop date Dose Dose Unit Frequency Route
Medical History Concomitant Diseases	Reported disease, condition or surgery term Standard medical name System organ class Year of diagnosis Active at screening (Y/N) Medication therapy (Y/N)
Treatment Exposure Data	Total number of days on therapy Number of tablets taken Number of tablets dispensed Number of tablets returned Number of tablets missed

¹ Subjects who are not included in the Confirmed Influenza population due to negative RT-PCR and culture assays will not be considered excluded from efficacy analysis

10. EFFICACY

10.1 General

Unless otherwise specified, all statistical tests will use two-sided tests at the $\alpha=0.05$ level.

The following definitions will apply to multiple efficacy analyses:

- Daily Diary Period Each daily diary period will begin 24 hours prior to the time of diary assessment and end at the time of diary assessment.
- Symptom Relief Medication Any medication taken for a symptom of influenza as indicated by the subject during the study period.

10.2 Primary Efficacy Analysis: Time to Symptom Response

The primary efficacy analysis will be the comparison of the time from first dose of study medication to symptom response between treatment groups using Kaplan-Meier survival curves and the Gehan-Wilcoxon test stratified by (1) time from onset of illness to time of first dose of study medication (0-24, >24-≤36, or >36 hours from onset), and (2) vaccination status (Y/N).

Definitions:

- Symptom Response The set of criteria to be defined based upon a blinded review of symptom scores (pooled for all influenza-infected subjects without regard to treatment group assignment) that correlate to the time at which subjects report that they return to usual health (a daily global assessment question). Methodology to be used for the derivation of the Symptom Response definition is described in section 10.2.1 below. Symptom scores must be maintained at the defined level for at least 2 daily diary periods without any symptom relief medication during or between those 2 daily diary periods.
- Time of Symptom Response The start of the first daily diary period in which Symptom Response is achieved and is maintained for at least two daily diary periods without any symptom relief medication during or between those two daily diary periods.
- Time to Symptom Response Time (hours) from the first dose of study medication to the Time of Symptom Response.

Variables Used for the Analysis

The primary efficacy analysis will require the following variables:

Variable	Source	Format/Notes
Date and time of first medication intake	CRF	
Date and time of completion for each symptom assessment record	Subject diary	
Symptom score assessment for each symptom for each diary record	Subject diary	The ordinal symptom severity, intensity or frequency score assessment for each of the 32 symptoms will be coded to numerical values 0-4.

Variable	Source	Format/Notes
		
It will not be possible for any individual symptom assessment to be missing within a diary record, therefore no individual item imputation will be required.
 
In the event that the diary was not completed at a specified time point (e.g., Day 2), the missing data will not be imputed.

Date and time of symptom relief medication intake	Sponsor-provided listing	The list of symptom relief medications will be selected from the listing of all concomitant medications prior to unblinding.

10.2.1 Derivation of the Symptom Response Definition

The Symptom Response definition will be derived based upon analysis of blinded daily FLU-PRO symptom scores and responses to the daily FLU-PRO question, “Have you returned to your usual health today?” for subjects with laboratory-confirmed influenza.

The Symptom Response definition will consist of a maximum response criterion (0, ≤1, ≤2, ≤3 or ≤4) for each of the 32 FLU-PRO items.

The objective of this procedure is to identify the Symptom Response definition that minimizes the diary-level misclassification rate between Symptom Response and Usual Health status as reported by the influenza-positive subjects enrolled in this study.

Procedure:

1. Evaluate whether each daily diary record has achieved return to usual health (requiring 2 consecutive daily diary assessments with “yes” response to the “usual health” question in FLU-PRO without use of symptom relief medication during or between those daily diary periods). This step will create a “Returned” variable with possible values of “Y” for each daily diary record that constitutes return to usual health and “N” for each daily diary record that does not.
2. Determine the set of possible Symptom Response definitions to be evaluated by selecting potential maximum response criteria that are likely to correlate well with return to usual health.
 - a. Examine the cumulative distribution of ordinal symptom assessment responses for the two consecutive diary records at which subjects return to Usual Health.
 - b. Maximum response criteria will be selected for consideration as part of the Symptom Response definition if they are included in the ≥90% - ≤95% cumulative distribution of symptom assessments at the time of return to usual health. If a maximum response criterion includes the 95th percentile and exceeds the 95% cumulative distribution, the criterion will still be selected for consideration.

For example, consider the following cumulative distribution of symptom ratings for the two consecutive diary records at which a fictional population of subjects return to usual health:

		Records Reporting 0	Records Reporting ≤1	Records Reporting ≤2	Records Reporting ≤3	Records Reporting ≤4
Coughing	N	300	455	478	485	500
	%	60.0%	91.0%	95.6%	97%	100%
Felt cold	N	480	499	500	500	500
	%	96.0%	99.8%	100%	100%	100%
(table would include all 32 FLU-PRO symptoms for maximum response criteria selection purposes)						

For “coughing”, the maximum symptom response criteria of ≤ 1 and ≤ 2 would be selected because the 90th percentile of responses is included in ≤ 1 and the 95th percentile is included in ≤ 2 . For “felt cold”, the maximum symptom response criterion of 0 would be selected because both the 90th and 95th percentiles are included in 0.

Possible Symptom Response definitions will be determined from the set of maximum response criteria selected.

3. For each possible Symptom Response definition, evaluate whether each daily diary record has achieved Symptom Response (two consecutive diary entries with all symptoms assessed \leq the maximum response values with no symptom relief medication intake during or between those two daily diary periods). This step will create a “Responded” variable with possible values of “Y” for each daily diary record that has achieved Symptom Response and “N” for each daily diary record that has not achieved Symptom Response. This step will be performed on a data storage/VM infrastructure that can support evaluation of 4.2 billion daily diary records with different possible Symptom Response definitions. If the number of diary record evaluations required (number of possible Symptom Response definitions multiplied by number of daily diary records to be evaluated) exceeds 4.2 billion, go back to step 2b above, and increase the $\geq 90\%$ cumulative distribution threshold by 0.1% increments until the number of possible maximum response criteria is reduced to a number that will result in evaluation of ≤ 4.2 billion daily diary records.
4. For each possible Symptom Response definition, determine the definition’s misclassification rate by comparing the “Responded” and “Returned” variables for each daily diary record. The percentage of daily diary records with mismatched “Responded” and “Returned” values (e.g., “Y” and “N”) will constitute that Symptom Response definition’s misclassification rate.
5. The Symptom Response definition returning the lowest misclassification rate will be selected as the Symptom Response definition for the study and will be used to calculate the primary efficacy parameter (time to Symptom Response) for each subject.
6. If two or more Symptom Response definitions produce the lowest misclassification rate (a “tie”), the Symptom Response definition with the lower sum of scores will be selected. In the event that the sum of scores are also equal, the Symptom Response definition with the smallest absolute difference between the proportion of false positives (“Responded” but not “Returned”) and false negatives (“Returned” but not “Responded”) will be selected. If there is still a tie, the definition with the lowest sum of maximum response values for the Body/Systemic domain will be selected, and if that is still a tie, the definition with the lowest sum of maximum response values for the Eye domain will be selected, and so on for the Gastrointestinal, Throat, Nose and Chest/Respiratory domains. If there is still a tie, list the items under the Body/Systemic, Eye,

Gastrointestinal, Throat, Nose and Chest/Respiratory domains in alphabetical order and compare the maximum response values until a definition with the lowest item score can be selected.

The Symptom Response Definition selected in this step will be applied for any subsequent analysis that calls for the primary efficacy analysis to be repeated unless otherwise specified.

10.2.2 Analysis of the Primary Efficacy Parameter

The primary efficacy parameter, time to Symptom Response, will be derived as follows:

Event: Time of Symptom Response – time of the first dose
 Censored: Time of last symptom assessment – time of the first dose

If Symptom Response is achieved at the time of the first symptom assessment diary record, the subject will be excluded from the analysis.

If Symptom Response is not achieved prior to a subject’s last available diary assessment, but the criteria are met at the last available diary assessment with no evidence of symptom relief medication intake during that diary period, time of Symptom Response will be considered to have occurred at the start of the last daily diary period.

Time to Symptom Response for the NTZ treatment group will be compared to that of the placebo treatment group using a Gehan-Wilcoxon test stratified for (1) time from onset of illness to time of first dose of study medication (0-24, >24-≤36, or >36 hours from onset), and (2) vaccination status (Y/N). The comparison will be graphically depicted using Kaplan-Meier curves.

Analysis Population(s):	Confirmed Influenza
Derived Variables:	Event: Time of symptom response – time of the first dose Censored: Time of last symptom assessment – time of the first dose

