1.2.6 Randomized Double-Blind Placebo Controlled Trial of NTZ in Treating Uncomplicated Influenza: Study RM08-3003

A Phase 3 randomized, double-blind, placebo controlled trial was conducted in 25 outpatient primary care clinics in the United States, Puerto Rico and Australia between December 2015 and August 2016. Three hundred twenty-four subjects 12 to 65 years of age were enrolled based upon symptoms and the presence of influenza in the community. Subjects were enrolled within 40 hours of symptom onset and randomized to receive NTZ 600 mg or placebo twice daily for five days. Nasopharyngeal swabs were collected at baseline for identification of respiratory pathogens by RT-PCR. All subjects either returned to the clinic or were visited daily by the study team to collect nasopharyngeal swabs on days 2, 3, 4 and 5 for quantitative influenza viral titer determination. Blood samples were collected on days 3 and 5 for population pharmacokinetics. Subjects maintained diaries to record time of medication intake, oral temperature, the severity of each of 7 symptoms (cough, nasal obstruction, sore throat, fatigue, headache, myalgia or feverishness graded as absent, mild, moderate or severe), ability to perform normal activities (scale of 0-10), time lost from work or school, concomitant medications and adverse events. Diary data was recorded twice daily through study day 14 or, if longer, until the subject no longer had any moderate or severe influenza symptoms. Subjects returned to the clinic for follow-up on day 7, day 14 and day 28. Blood and urine samples were collected at baseline and day 7 for lab safety tests, and blood samples were collected at baseline and day 28 for influenza antibody titer. Nasopharyngeal swabs were collected from all subjects at days 7 and 14 for identification of viruses and for quantitative influenza viral titer. The primary efficacy endpoint was time from first dose to alleviation of symptoms (all 7 symptoms absent or mild and remained so for at least 21.5 hours). The primary efficacy analysis was a comparison of times from first dose to symptom alleviation for subjects in the NTZ and placebo treatment groups with laboratory-confirmed influenza at baseline, day 2 or day 3. The analysis was performed using a Prentice Wilcoxon test with an alpha of 0.05.

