4.1 Inclusion Criteria

- 1) Male and female subjects at least 12 years of age
- 2) Presence of clinical signs and/or symptoms consistent with an acute illness compatible with influenza infection (each of the following is required):
 - a) oral temperature of $\geq 99.4^{\circ}\text{F}$ or $\geq 37.4^{\circ}\text{C}$ (obtained in office or self-measured within 12 hours prior to screening – if self-measured, subject must also have taken an antipyretic within 4 hours prior to screening), AND
 - b) at least one of the following respiratory symptoms (cough, sore throat, nasal obstruction), AND
 - c) at least one of the following constitutional symptoms (fatigue, headache, myalgia, feverishness).
- 3) Confirmation of influenza A or B infection in the local community by one of the following means: (a) the institution's local laboratory, (b) the local public health system, (c) the national public health system, or (d) a laboratory of a recognized national or multinational influenza surveillance scheme

- 4) Onset of illness no more than 40 hours before enrollment in the trial
Note: Time of onset of illness is defined as the earlier of:
 - a) the time when the temperature was first measured as elevated, OR
 - b) the time when the subject experienced the presence of at least one respiratory symptom AND the presence of at least one constitutional symptom.
- 5) Willing and able to provide written informed consent (including assent by legal guardian if under 18 years of age) and comply with the requirements of the protocol, including completion of the patient diary

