8.4.1 Efficacy Analyses

Efficacy analyses will be based on a population consisting of all subjects that received at least one dose of study drug and had laboratory-documented influenza infection (infected intent-to-treat or ITTI population). Laboratory-documented influenza infection is defined by identification of influenza virus in nasopharyngeal secretions by RT-PCR or viral culture at baseline, day 2 or day 3.

There will be one primary efficacy analysis:

- Time to Symptom Response for the NTZ treatment group will be compared to that of the placebo treatment group using a stratified Gehan-Wilcoxon test ($\alpha = 0.05$) stratified by (1) time since symptom onset for each subject at enrollment (≥ 24 hours, $>24 - 36$ hours, >36 hours) and (2) whether the subject received seasonal influenza vaccination after August 1, 2018. Subjects without a Symptom Response being recorded will be treated as censored as of their last diary without a documented Symptom Response.

If the primary analysis is significant at the 0.05 level, a key secondary efficacy analysis will be formally evaluated at the 0.05 level as follows:

- Time to Ability to Perform All Normal Activities for the two treatment groups will be compared using a stratified Gehan-Wilcoxon test ($\alpha = 0.05$) stratified by (1) time since symptom onset for each subject at enrollment (≥ 24 hours, $>24 - 36$ hours, >36 hours) and (2) whether the subject received seasonal influenza vaccination after August 1, 2018. Subjects without an Ability to Perform All Normal Activities response being recorded will be treated as censored as of their last diary without a documented Ability to Perform All Normal Activities response.

If both the primary analysis and the key secondary efficacy analysis are significant at the 0.05 level, another secondary efficacy analysis will be formally evaluated at the 0.05 level as follows:

- Proportions of subjects experiencing one or more complications of influenza including pneumonia, otitis media, bronchitis, sinusitis, worsening of pre-existing health conditions, systemic antibiotic use for infections secondary to influenza infection, hospitalization due to influenza or complications of influenza and death will be compared between the treatment groups using a Fisher's exact test ($\alpha = 0.05$).

A third secondary analysis will be performed as follows:

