7.3 Sample Size Justification

The Symptom Response definition for this study will be derived from the subjects' FLU-PRO questionnaire responses as described in section 10.2.1 below. The FLU-PRO-derived endpoint is expected to track very closely to return to usual health status (a daily yes/no question in the FLU-PRO questionnaire). Patient-reported outcomes for time to return to usual health status have been shown to track very closely with time to ability to perform 100% of usual activities.^{1,2,3} We assume, therefore, that the cumulative distributions of time to symptom response for the placebo treatment group will closely reflect historical data (Romark studies RM08-3002 and RM08-3003 and oseltamivir studies WV15670 and WV15671) for time from first dose until the subjects report that they are able to perform 100% of usual activities. Based upon data from Romark studies RM08-3001, RM08-3002 and RM08-3003, we assume that treatment with NTZ should result in reduction of at least 40 hours in median time to symptom response with differences being less at the first quartile and greater at the third quartile. Based upon this historical data, the following curves have been developed for determining sample size.

Based upon these curves, a sample size of 552 subjects with laboratory-confirmed influenza (i.e. 276 for each of the 2 groups) will provide 90% power to detect a statistically significant difference in the survival distributions between NTZ and placebo groups (2-sided alpha of 0.05). This calculation was performed for the Gehan rank test using SAS PROC POWER (SAS 9.4) with the curves shown above (proportion not recovering by the end of each day was used as input) and censoring at day 21 (hour 504). Assuming that 8% of subjects will have incomplete data, we arrive at a sample size of 600 subjects in total, 300 per treatment group.

Based upon these calculations, the study will enroll at least 600 subjects with laboratory-confirmed influenza up to a maximum of 700 subjects with laboratory-confirmed influenza. We estimate that this will require enrollment of 800 to 1,200 subjects in total assuming a flu-positive rate between 50% and 75%.

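### The 90% power at 552 is for a Gehan test with no strata; the planned six-cell stratified Gehan test may fall below 90% at the minimum enrolment of 600

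*SAP*

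**What the plan says.** The primary test in SAP 10.2.2 is made "using a Gehan-Wilcoxon test stratified for (1) time from onset of illness to time of first dose of study medication" (0-24, >24-≤36, >36 hours) and for vaccination status (Y/N), so 3 × 2 = 6 cells. Protocol 8.4.1 plans the same kind of test: the NTZ group "will be compared to that of the placebo treatment group using a stratified Gehan-Wilcoxon test". The key secondary (SAP 10.4.1) and modified-response (SAP 10.4.3) analyses use the same form. Neither document says how the strata are combined or weighted.

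The sample size rests on a simpler test. To reach 90% power at a two-sided alpha of 0.05, SAP 7.3 and Protocol 8.1 call for "a sample size of 552 subjects with laboratory-confirmed influenza (i.e. 276 for each of the 2 groups". On method, the SAP says: "This calculation was performed for the Gehan rank test using SAS PROC POWER (SAS 9.4". Strata, stratum sizes and stratum effects are not mentioned.

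Three further facts bear on stratum sizes:
- Protocol 4.1 requires "Onset of illness no more than 40 hours before enrollment in the trial".
- Recent seasonal vaccination was an exclusion until Amendment 3, which produced protocol version 1.5 of January 3, 2019 (Protocol Appendix IV). The trial was expected to run from December 2017 to April 2019.
- Randomization was stratified by onset time but not by vaccination (Protocol 6).

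**The concern.** The Gehan weight at each event time is the number at risk. In a stratified test it is the number at risk within the stratum, so unless it is rescaled, a stratum's influence grows faster than its share of subjects. If vaccination is spread evenly over onset time and 10% are vaccinated, the vaccinated cells carry 0.1²/(0.1² + 0.9²) = 1.2% of the total weight. Information from small cells is largely wasted, and a power figure for a test without strata does not carry over.

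Power is what is at stake, not validity. The key secondary analysis is formally tested only if the primary is significant (SAP 10.4), so a missed primary costs that claim too.

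**Working it through.** **Inputs from the documents.** 90% power, two-sided alpha 0.05, 552 subjects allocated 1:1, 8% incomplete, 600 to 700 confirmed cases. Protocol 8.1 analyses all 600, with incomplete subjects censored.

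**The plan's own figures.** 552/0.92 = 600 reproduces. So do 600/0.75 = 800 and 600/0.50 = 1,200. The 552 itself cannot be checked, because the calculation was run "with the curves shown above (proportion not recovering by the end of each day was used as input" and those curves are in a figure that is not available here. I therefore take 90% at 552 as given. It implies a noncentrality of 1.960 + 1.282 = 3.2415.

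**Formula.** Let stratum s hold a share p of the subjects, with a common treatment effect. With raw at-risk weights, its statistic has a mean proportional to p² and a variance proportional to p³. Summing over strata gives, relative to a single test without strata,

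E = (Σp²)² / Σp³,

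which is 1 for equal strata and below 1 otherwise. Power at N is Φ(3.2415·√(E·N/552) − 1.960). If each stratum's weights are divided by its size plus one, mean and variance are both roughly proportional to p, and E returns to about 1.

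**Why unequal strata are expected.** The top onset band covers about 36 to 40 hours, plus any delay to first dose, against 24 and 12 hours for the other two. Recently vaccinated subjects could enter only in the last months.

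**One case in full.** Take onset 45/35/20 with 10% vaccinated (assumed). The cells are 0.405, 0.315, 0.18, 0.045, 0.035 and 0.02. Then Σp² = 0.2993, Σp³ = 0.10366 and E = 0.2993²/0.10366 = 0.864. At 600, 3.2415·√(0.864·600/552) − 1.960 = 1.18, so power is 88%. The 600 subjects work like 0.864 × 600 ≈ 519.

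**Range** (all shares assumed, strata not prognostic):

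| Onset shares | Vaccinated | E | 552 | 600 | 700 |
|---|---|---|---|---|---|
| Six equal cells | 50% | 1.00 | 90% | 92% | 95% |
| Equal thirds | 5% | 0.96 | 89% | 91% | 95% |
| Equal thirds | 10% | 0.92 | 88% | 90% | 94% |
| 45/35/20 | 10% | 0.86 | 85% | 88% | 92% |
| 45/35/20 | 20% | 0.83 | 84% | 87% | 92% |
| 60/30/10 | 10% | 0.80 | 83% | 86% | 90% |
| 60/30/10 | 20% | 0.77 | 81% | 84% | 89% |

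The 60/30/10 split is what onset times uniform over 0-40 hours would give. Holding 90% needs E of at least 552/600 = 0.92 at 600, or 552/700 = 0.79 at 700.

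**Simulation check.** 20,000 trials per case, log-normal curves with a 40-hour median reduction, placebo median 160 hours, log-SD calibrated to 90% at 552; N = 600 with 8% dropout:

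| Case | No strata | Stratified, raw Gehan | Stratified, size-scaled |
|---|---|---|---|
| 45/35/20, 10% vaccinated | 92.3% | 87.7% | 91.9% |
| Same, prognostic strata (log-time shifts of 0.25) | 92.1% | 88.9% | 92.6% |
| 60/30/10, 10% vaccinated | 91.7% | 85.0% | 91.5% |
| Equal thirds, 50% vaccinated | 92.2% | 91.5% | 91.7% |

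A separate simulation of 3,000 trials per setting (log-normal medians 200 and 160 hours, 600 subjects, 8% dropout) gave 86-87% for raw stratified Gehan and 92% for stratified Peto-Prentice or size-scaled weights. Null rejection was 0.050-0.052 for all of them.

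**The case against.** Several points on the other side stand.

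- **Shares are unknown.** A reader might infer that the strata are very unequal by design. The documents set no quota and give no expected split, and the width of an onset band is not its share of enrolment. Imbalance is a reasonable expectation, not a stated fact.
- **The loss depends on the stratum definitions.** It is zero for equal cells and does not rise steadily with imbalance. For vaccination alone, E is 0.955 at 5% vaccinated, 0.92 at 10%, 0.89 at 20% and 1 at 50%. Protocol 8.4.1 defines vaccination as after August 1, 2018 while SAP 10.2.2 says only Y/N, so the coding of earlier vaccinees affects the shares.
- **552 is not the analysed number.** At 600 to 700 a test without strata would have 92% to 95%, which offsets part or all of the loss.
- **Stratification can pay.** Prognostic strata remove between-stratum variation, so it is wrong to say that nothing is gained. In the simulated prognostic case raw Gehan rose from 87.7% to 88.9% at 600. Size-scaled weights keep that benefit and still did better, at 92.6%.
- **The weighting is inferred.** The documents name SAS but not the procedure or the rule for combining strata.
- **The planned test is valid.** Changing it amends a pre-specified analysis in a plan that cites FDA discussions.

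These points limit the size and certainty of the loss. They do not remove the mismatch between the test that was powered and the test that is planned.

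**Conclusion.** The point holds in a limited form. The stated 90% at 552 belongs to a Gehan test with no strata, not to the planned six-cell test. With raw at-risk weights and the assumed shares, E is about 0.77-0.96 and power about 84-91% at 600 and 89-95% at 700. A reader might go further and conclude that the trial will not reach 90%. The documents do not support that: with equal strata, with sufficiently prognostic strata, or with enrolment near 700, it may. The figures rest on the sponsor's 90% at 552 taken as given, assumed stratum shares, a common effect across strata, and summed at-risk weights. It is worth acting on because the loss is avoidable: where strata were unequal, size-independent weights on the same strata recovered most or all of it.

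**What to change.** Before unblinding, keep the strata but specify weights that do not grow with stratum size. Either a stratified Peto-Prentice test or Gehan weights divided by stratum size plus one would serve. State the choice in SAP 10.2.2, 10.4.1 and 10.4.3 and in Protocol 8.4.1; the sensitivity analyses in SAP 10.3 repeat the primary and would follow. There is precedent in the programme for the first option: of RM08-3003, Protocol 1.2.6 says "The analysis was performed using a Prentice Wilcoxon test with an alpha of 0.05".

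If raw Gehan weights are kept, say so, and replace 90% at 552 with power for the stratified test at 600-700, giving the expected stratum shares.

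The cost is a wording amendment to the pre-specified test in both documents and a small programming change. No new data are needed.
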